6.1.5 Definition of Biomarker Variables

- Minimal Residual Disease (MRD)

MRD will be analyzed from bone marrow and blood samples by a Sponsor-designed central laboratory. Samples will be analyzed for FLT3 mutational status at screening/baseline and EOT, and may be analyzed for FLT3 mutational status at other time points. Samples may be analyzed for mutations in AML related genes and changes in proteins in relation to treatment effects at screening/baseline and EOT, and may be analyzed for mutations in AML related genes and changes in proteins in relation to treatment effects at other time points.

FLT3/ITD mutation ratio will be measured in relation to total FLT3. For a subject with multiple ITD mutations, the overall FLT3/ITD mutation ratio will be calculated from the sum of all ITD mutations. Changes in FLT3/ITD mutation ratio from baseline will be compared.

At each visit, the presence of MRD will be “Present” if log₁₀-transformed overall FLT3/ITD mutation ratio is greater than -4; otherwise, the presence of MRD will be “Absent”. For subjects with multiple ITD mutations detected, the ratios will be summed.

Additional absolute cut points (e.g., log₁₀-transformed overall FLT3/ITD to total FLT3 ratio of -2, -3, etc.) may be evaluated, as well as the log₁₀ transformed change in FLT3/ITD to total FLT3 ratio at each visit compared to baseline.

Further details of biomarker variables will be specified in a separate biomarker analysis plan.

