FMS-like tyrosine kinase 3 (FLT3) is a member of the class III receptor tyrosine kinase family that is normally expressed on the surface of hematopoietic progenitor cells. FLT3 and its ligand play an important role in proliferation, survival and differentiation of multipotent stem cells. FLT3 is overexpressed in the majority of AML cases. In addition, activated FLT3 with internal tandem duplication (ITD) in and around the juxtamembrane domain and tyrosine kinase domain mutations at around D835 in the activation loop are present in 28% to 34% and 11% to 14% of AML cases, respectively [[Schlenk & Döhner, 2009](#)] transforming activity in cells [[Yamamoto et al, 2001](#)]. Patients with FLT3-ITD mutation show poor prognosis in clinical studies, with a higher relapse rate, a shorter duration of remission from initial therapy (6 months versus 11.5 months for those without FLT3-ITD mutations), as well as reduced disease-free survival (16% to 27% versus 41% at 5 years) and OS (15% to 31% versus 42% at 5 years) [[Patel et al, 2012](#); [Gale et al, 2008](#); [Yanada et al, 2005](#); [Tiesmeier et al, 2004](#); [Moreno et al, 2003](#)]. The incidence of relapse after hematopoietic stem cell transplant (HSCT) is also higher for patients with FLT3-ITD (30% versus 16% at 2 years for those without FLT3-ITD mutations) [[Brunet et al, 2012](#)]. Similar to their prognosis for first-line therapy, patients with relapsed/refractory FLT3-mutation positive AML have lower remission rates with salvage chemotherapy, shorter durations of remission to second relapse and decreased OS relative to FLT3-mutation negative patients [[Konig & Levis, 2015](#); [Chevallier et al, 2011](#); [Levis et al, 2011](#)].

In a recent international randomized phase III study of elacytarabine versus investigator choice in patients with relapsed/refractory AML, the CR rate in the control arm was only 12% [[Roboz et al, 2014](#)]. In this study, the treatment options available in the control arm (physician's choice) reflect contemporary clinical practice, rather than a strict selection of only patients that are eligible for intensive salvage regimens. As a result, this control arm should more appropriately represent what can be expected in standard clinical practice.

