AXL, a receptor tyrosine kinase, has been detected in AML and has been shown to play a role in mediating migration and invasiveness of cancer cells. Inhibition of AXL has been shown to increase apoptosis and inhibit proliferation of FLT3-ITD and FLT3 wild-type AML cell lines and primary AML cells in vitro and reduced tumor burden and prolonged survival in mouse models [[Janning et al, 2015](#)].

Gilteritinib

XOSPATA (gilteritinib) tablets have been approved by FDA, EMA and MHLW for the treatment of adult patients who have relapsed or refractory AML with a FLT3 mutation.

Gilteritinib has an inhibitory effect on tyrosine kinases, mainly FLT3, AXL, LTK and ALK.

Gilteritinib demonstrated favorable efficacy in a nonclinical AML model, with complete regression of tumors in the xenograft model mice transplanted with MV4-11, by repeated oral doses. In addition, gilteritinib inhibited the growth of Ba/F3 cells expressing either FLT3-ITD, FLT3-D835Y or FLT3-ITD-D835Y with similar activities. Gilteritinib has been studied in relapsed or refractory AML patients in a phase 1/2 study. In the study, patients with FLT3 mutated AML receiving 80 mg or higher dose had a complete composite remission (CRc) rate of 41% and median OS of 31 weeks [[Perl et al, 2017](#)]. Furthermore, 16% of the patients tested were in complete molecular remission by FLT3-ITD based minimal residual disease (MRD) assay [[Levis 2018](#)]. Based on promising activity observed in the phase 1/2 study in AML patients, a phase 3 study in relapsed or refractory AML is currently ongoing.

Programmed Death-Ligand 1/PD-1 Inhibitors

Agents that target the programmed death-ligand 1 (PD-L1)/PD-1 axis have shown broad activity and durable responses in multiple tumor types, holding the promise of delivering immune-based therapy to almost all patients with cancer. To date, patients with solid tumors have been the focus of most clinical studies that use immune checkpoint inhibitors; however, data are emerging that these therapeutics are active in hematological malignancies.

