3.2 Inclusion Criteria

Subject is eligible for the study if all of the following apply:

1. Institutional Review Board (IRB)/Independent Ethics Committee (IEC)-approved written informed consent and privacy language as per national regulations (e.g., Health Insurance Portability and Accountability Act Authorization for US sites) must be obtained from the subject or legally authorized representative prior to any study-related procedures (including withdrawal of prohibited medication, if applicable).
2. Subject is considered an adult according to local regulation at the time of signing informed consent form (ICF).
3. Subject has defined AML by the WHO criteria (2017) and fulfills one of the following:
 - Refractory to at least 1 cycle of induction chemotherapy
 - Relapsed after achieving remission with a prior therapy
4. Subject is positive for FLT3 mutation in bone marrow or blood after completion of the subject's last interventional treatment as determined by the local institution.
5. Subject has an ECOG performance status ≤ 2 at screening.
6. Subject must meet the following criteria as indicated on the clinical laboratory tests:
 - Serum AST and ALT ≤ 2.5 x upper limit of normal (ULN)
 - Serum total bilirubin (TBL) ≤ 1.5 x ULN
 - Serum creatinine ≤ 1.5 x ULN or an estimated glomerular filtration rate of > 50 mL/min as calculated by the Modification of Diet in Renal Disease equation.
7. Subject is suitable for oral administration of study drug.
8. A female subject is eligible to participate if she is not pregnant [see [Appendix 12.3 Contraception Requirements](#)] and at least one of the following conditions applies:
 - Not a woman of childbearing potential (WOCBP) as defined in [[Appendix 12.3 Contraception Requirements](#)]

OR

- WOCBP who agrees to follow the contraceptive guidance as defined in [Appendix 12.3 Contraception Requirements] throughout the treatment period and for at least 180 days after the final study drug administration.
9. Female subject must agree not to breastfeed starting at screening and throughout the study period, and for at least 180 days after the final study drug administration.
 10. Female subject must not donate ova starting at screening and throughout the study period, and for at least 180 days after the final study drug administration.
 11. A male subject must not donate sperm starting at screening and throughout the treatment period, and for at least 120 days after the final study drug administration.

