5.7.2 Exploratory Biomarker

Bone marrow aspirate samples

Samples will be analyzed for MRD at any time point. Samples will be analyzed for FLT3 mutational status at screening/baseline and EOT, and may be analyzed for FLT3 mutational status at other time points. Samples may be analyzed for mutations in AML related genes and changes in proteins in relation to treatment effects at screening/baseline and EOT, and may be analyzed for mutations in AML related genes and changes in proteins in relation to treatment effects at other time points. Samples may be used for method development or validation of diagnostic assays related to study treatment.

Blood samples

Samples may be analyzed for MRD at any time point. Samples may be analyzed for FLT3 mutational status at screening/baseline and EOT, and may be analyzed for FLT3 mutational status at other time points. Samples may be analyzed for mutations in AML related genes and changes in proteins in relation to treatment effects at screening/baseline and EOT, and may be analyzed for mutations in AML related genes and changes in protein expression in relation to treatment effects at other time points.

Samples will be assessed for activation status of FLT3 and AXL, AML blast cell phenotyping and immunophenotyping for immune cell populations including, but not limited to, lymphocyte subsets, dendritic cells, natural killer cells, regulatory T cells and T lymphocyte subsets. Samples may be used for method development or validation of diagnostic assays related to study treatments.

Bone marrow/blood sampling, processing, storage and shipment instructions will be provided in the Laboratory Manual. Samples will be shipped to and analyzed by a sponsor-designated analytical laboratory. Samples will be stored for a period up to 15 years following study

database hard lock. Please refer to the Laboratory Manual for more detailed information on this topic.

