5.4 Biomarker Analysis Set (BMAS)

The biomarker analysis set (BMAS) will include the subjects from the administered population for whom sufficient biomarker measurements were collected.

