7.4.3 Analysis of Exploratory Efficacy Endpoint

- Evaluate efficacy of gilteritinib given in combination with atezolizumab in terms of minimal residual disease (MRD). MRD analysis will be conducted on the BMAS. MRD will be assessed in relation to the following efficacy variables:
 - CR rate
 - CRc rate
 - EFS
 - Duration of remission
 - OS
- Evaluate potential genomic, proteomic and/or other biomarkers that may correlate with treatment outcome
- Evaluate pharmacodynamic biomarkers of treatment effect
- Evaluate immune cell populations and AML blasts by immunophenotyping in relation to treatment effects

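### The exploratory MRD rule looks only at FLT3-ITD, so a subject whose sole FLT3 mutation is in the kinase domain is classed MRD-absent at every visit

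*SAP*

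**What the plan says.** SAP 6.1.5 builds MRD from one quantity: "FLT3/ITD mutation ratio will be measured in relation to total FLT3". Where several ITD mutations are found, they are summed. MRD is Present at a visit when the log10 "overall FLT3/ITD mutation ratio is greater than -4; otherwise, the presence of MRD will be" Absent. The optional extra cut points and the change from baseline use the same ITD ratio. The section has no kinase-domain term, no not-evaluable category and no condition that ITD was found at baseline. It leaves further details to a separate biomarker analysis plan.

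Inclusion criterion 4 (Protocol 3.2) requires only this: "Subject is positive for FLT3 mutation in bone marrow or blood". Protocol 1.1 names two kinds of activating FLT3 mutation, ITD and kinase-domain mutations around D835, which "are present in 28% to 34% and 11% to 14% of AML cases, respectively".

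SAP 7.4.3 runs the MRD analysis on the biomarker analysis set (BMAS) and states that "MRD will be assessed in relation to the following efficacy variables": CR rate, CRc rate, EFS, duration of remission and OS. SAP 5.4 defines that set as treated subjects "for whom sufficient biomarker measurements were collected". On baseline testing, Protocol 5.7.2 says of marrow aspirates: "Samples will be analyzed for FLT3 mutational status at screening/baseline and EOT".

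**The concern.** The rule has two outcomes, and everything that is not Present is Absent. For a subject who had ITD at baseline, Absent means the ITD clone has fallen to or below the cut. For a subject who never had ITD, Absent means only that the assay has no target. The two receive the same label.

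The planned analyses relate MRD status to remission and survival outcomes. Kinase-domain-only subjects would enter the Absent group whether or not they responded, which can weaken or distort any association between MRD clearance and outcome. If true ITD clearance is uncommon, a modest number of such subjects could make up much of that group.

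**Working it through.** The plan states no figure for this point, so there is nothing to reproduce. The check has two parts.

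**1. Apply the rule as written.** The cut of −4 on the log10 scale is a ratio of 0.0001.

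| ITD / total FLT3 ratio | Result under SAP 6.1.5 |
|---|---|
| 0.4 | Present |
| 0.001 | Present |
| 0.00011 | Present |
| 0.0001 | Absent (not greater than the cut) |
| 0, log undefined | Absent, through the 'otherwise' clause |
| no ratio available | Absent, through the 'otherwise' clause |

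A kinase-domain-only subject has a ratio of 0 at every visit and is therefore Absent throughout, screening included.

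**2. Size the group.** Inputs from Protocol 1.1: ITD prevalence *I* = 28–34% and kinase-domain prevalence *T* = 11–14% of AML cases. Assumption: a fraction *f* of kinase-domain cases also carry ITD. The documents do not give *f*, so it is varied. Every subject is assumed to be in the BMAS.

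Kinase-domain-only share of FLT3-mutated subjects: *s* = *T*(1 − *f*) / [*I* + *T*(1 − *f*)]. The low end uses *T* = 11, *I* = 34; the high end uses *T* = 14, *I* = 28.

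| *f* | *s*, low | *s*, high | Of 49 (full phase 2) | Of 22 (stopped at stage 1) |
|---|---|---|---|---|
| 0 | 11/45 = 24.4% | 14/42 = 33.3% | 12.0–16.3 | 5.4–7.3 |
| 0.5 | 5.5/39.5 = 13.9% | 7/35 = 20.0% | 6.8–9.8 | 3.1–4.4 |
| 1 | 0 | 0 | 0 | 0 |

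**Illustration of the effect on the Absent group.** Protocol 1.1 reports that in an earlier gilteritinib study "16% of the patients tested were in complete molecular remission by FLT3-ITD based minimal residual disease (MRD) assay". Suppose that 16% held among the ITD subjects here.

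- Overall Absent proportion = *s* + (1 − *s*) × 0.16.
  - *f* = 0.5: 0.139 + 0.861 × 0.16 = 27.7%, up to 0.200 + 0.800 × 0.16 = 32.8%.
  - *f* = 0: 0.244 + 0.756 × 0.16 = 36.5%, up to 0.333 + 0.667 × 0.16 = 44.0%.
  - *f* = 1: 16.0%.
- Kinase-domain-only part of the Absent group = *s* / [*s* + (1 − *s*) × 0.16].
  - *f* = 0.5: 50.3–61.0%.
  - *f* = 0: 66.9–75.8%.

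**The case against.** The strongest reply is that SAP 6.1.5 leaves further details to a biomarker analysis plan, and SAP 5 leaves detailed set criteria to Classification Specifications. Neither document is available, and either could limit MRD to subjects with baseline ITD. That possibility stands, so it is not established that subjects will in fact be misclassified. But the SAP already states a complete two-way rule, and a programmer who follows it obtains the result above. A later restriction would have to override that wording.

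A second reply is that an undefined log ratio is missing data, and SAP 7.1 bases percentages on subjects without missing data, so these subjects would drop out. This does not work. A subject who truly clears ITD also has a zero ratio and an undefined log. The 'otherwise' clause must cover that subject, or full clearance could never be recorded, and the SAP gives no way to treat the two zeros differently.

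Third, the references to change from baseline and to summed ITD mutations suggest that the authors had ITD-positive subjects in mind. That is plausible, but the SAP does not say so.

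Fourth, the size is poorly determined, and this stands. The prevalences are for AML in general, the overlap is assumed, the BMAS size is not stated, and the 16% comes from another study. The SAP does not explicitly call for a table of MRD-absent rates, and no effect on a planned association has been calculated. The percentages are illustrations only.

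Finally, MRD is exploratory, and baseline FLT3 testing would allow the subjects to be separated at analysis. Both are true; they limit the weight of the point and make it cheap to fix.

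The revision history in SAP 8 mentions removal of an MRD biomarker analysis, but the current text of 6.1.5 and 7.4.3 still defines and analyses MRD.

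**Conclusion.** The concern holds as a defect in the rule stated in the SAP. Under that rule, a subject with only a kinase-domain mutation can never be MRD-present, and nothing in the SAP takes such subjects out of the analysis. How many there will be is unknown: anywhere from none to about a third of FLT3-mutated subjects, depending on the ITD/kinase-domain overlap and on whether general AML prevalences carry over to relapsed or refractory disease.

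The damage is confined to the exploratory MRD analyses. The primary CRc analysis, the Simon two-stage decision and the secondary endpoints do not depend on this rule. The SAP should be corrected because the analysis cannot be interpreted as specified. Confidence is medium, since the unseen biomarker analysis plan may already settle the point.

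**What to change.** In SAP 6.1.5, derive Present or Absent only for subjects in whom the central assay detects FLT3-ITD at baseline. Class all others as not evaluable for ITD-based MRD. State that a measured zero ratio in an evaluable subject is Absent, and that a missing ratio is missing. In SAP 7.4.3, name this subset of the BMAS as the MRD denominator and report its size.

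If the biomarker analysis plan already contains these rules, replace the 'otherwise' wording in SAP 6.1.5 with a cross-reference to that plan.

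The cost is SAP wording only. FLT3 mutational status at screening or baseline is already to be measured, so no new sample, visit or assay is needed. The price is a smaller MRD denominator.

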6.2 Safety Variables

Safety (Development of DLTs and AEs) are the primary endpoints of the study.

The safety and tolerability of ASP2215 will be assessed using:

- Development of DLT
- Adverse events
- Clinical laboratory results (chemistry, hematology, coagulation, urinalysis, serum pregnancy test and bone marrow)
- Vital signs (systolic and diastolic blood pressure, pulse rate and body temperature)
- 12-lead electrocardiogram (ECG)
- Eastern Cooperative Oncology Group (ECOG) performance status scores

6.2.1 Definition of DLT

In Phase 1, a DLT is defined as any of the following events that occur during the observation period (cycle 1/day 1 through cycle 1/day 28) and that is considered to be possibly or probably related to study regimen. In Phase 2, the DLT observation period is the first treatment cycle (cycle 1/day 1 through cycle 1/day 28).

- Confirmed Hy's law case
- Any Grade ≥ 3 non-hematologic or extramedullary toxicity with the following exceptions:
 - Anorexia or fatigue
 - Grade 3 nausea and/or vomiting if not requiring tube feeding or TPN, or diarrhea if not requiring or prolonging hospitalization that can be managed to grade ≤ 2 with standard antiemetic or antidiarrheal medications used at prescribed dose within 7 days of onset
 - Grade 3 mucositis that resolved to grade ≤ 2 within 7 days of onset
 - Grade 3 fever with neutropenia, with or without infection*
 - Grade 3 infection*
 - Grade 3 infusion-related toxicity, if successfully managed and resolves within 72 hours.

*Toxicities are excluded only if the event is an expected direct complication of cytopenias due to the active underlying leukemia.

Hematologic toxicity will not be considered as a DLT. However, prolonged myelosuppression defined as absolute neutrophil count (ANC) $\leq 0.5 \times 10^9/L$ for more than 21 days from the onset of severe neutropenia in the absence of evidence of active leukemia in the marrow or blood will be considered as a DLT.

6.2.2 Definition of MTD

MTD is defined as the highest dose level where no more than one subject out of six eligible subjects has experienced DLT during the DLT observation period.

6.2.3 Bayesian Posterior Probability for Safety Monitoring in Phase 2

A Bayesian posterior probability will be used for safety monitoring during the whole treatment period. Subjects in phase 1 and phase 2 cohorts who complete the DLT observation period or experience DLTs will be included in the model-fitting process to provide the complete safety information. The estimated DLT rates based on the Bayesian beta-binomial model will be provided for safety monitoring in the dose expansion cohort. If the DLT rate for the expanded dose level is equal or higher than 25% with a posterior probability of 80%, then the enrollment to the expansion cohort will be paused and the safety will be reassessed by the DEC. If the reassessment warrants, enrollment to the expansion cohort may be continued at the current dose level or 1 lower dose level. Safety evaluation will be conducted separately for induction, consolidation and maintenance phases.

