2.2.2 Dose Rationale

In the first-in-human phase 1/2 clinical study 2215-CL-0101, relapsed/refractory AML subjects were treated with gilteritinib at doses ranging from 20 to 450 mg administered once daily. The primary objectives for this study were to determine the safety and pharmacokinetics of gilteritinib following single and repeat dosing. In addition, preliminary efficacy as assessed by response rates was evaluated.

Clinical safety data indicated an MTD of 300 mg. Clinical efficacy data supports doses of 120 mg and greater to ensure efficacy in FLT3-mutation positive subjects. PIA has shown substantial reduction of phospho-FLT3, with > 90% inhibition at doses of 80 mg or greater. Although, none of the dose levels within the expansion cohort reached the threshold to stop enrollment (> 20% DLT with posterior probability of 80%), 120 mg and 200 mg doses especially had low DLT rates. However, CK and AST elevations correlating with increasing dose and increasing exposure were observed. Overall, 120 mg provides a good balance of

ensuring effective drug levels for virtually all subjects with a low incidence of safety concerns.

Doses of 80 mg and 120 mg gilteritinib given in combination with atezolizumab is chosen as a starting dose for the escalation cohort to maintain a more efficacious gilteritinib dose while confirming the safety of the combination in a population that is not able to tolerate intense therapy.

For atezolizumab, simulations [Bai et al, 2012] do not suggest any clinically meaningful differences in exposure following a fixed dose compared with a body weight-adjusted dose. On the basis of this analysis, a fixed dose of 1200 mg once every 3 weeks (equivalent to a weight based dose of 15 mg/kg once every 3 weeks) was defined as the RP2D.

For the once every 2 weeks dosing interval, the fixed dose of 840 mg once every 2 weeks is expected to be equivalent to that of 1200 mg every 3 weeks, the approved dosage for atezolizumab [Tecentriq prescribing information, 2016]. A 2-week dosing schedule is being used to better align AML treatment and evaluation schedule with gilteritinib. The fixed dose of 1200 mg once every 3 weeks (equivalent to an average body-weight based dose of 15 mg/kg once every 3 weeks) was selected on the basis of both nonclinical studies [Deng et al, 2016] and available clinical pharmacokinetic, efficacy and safety data (refer to the Atezolizumab IB for details).

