7.1 Sample Size

This is an open-label, single arm study. No interim analysis and 1 final analysis are planned.

Phase 1

The sample size in phase 1 is based on 3+3 design and not based on power calculation.

Phase 2

Simon's 2-stage design [Simon, 1989] will be used in the study to evaluate the efficacy in terms of CRc rate for the selected combination dose level of gilteritinib and atezolizumab. The null hypothesis that the true CRc rate is 50% will be tested against a 1-sided alternative. In the first stage, the CRc of 22 subjects will be evaluated. If there are 11 or fewer subjects with CRc from these 22 subjects by the end of cycle 2, the study will be stopped. Otherwise, 27 additional subjects will be accrued for a total of 49 subjects evaluable for calculation of CRc rate. The null hypothesis will be rejected if 32 or more subjects with CRc are observed in the 49 subjects by the end of cycle 2. This design yields a 1-sided type I error rate of 0.025 and power of 80% when the true CRc rate is 70%. The sample size was calculated in East[®] Version 6.4.

Bayesian Posterior Probability for Safety Monitoring in Phase 2:

A Bayesian posterior probability will be used for safety monitoring during the whole treatment period. Subjects in phase 1 and phase 2 cohorts who complete the DLT observation period or experience DLTs will be included in the model-fitting process to provide the complete safety information. The DLT rate will be reviewed as the last subject of each cohort of 7 DLT-evaluable subjects completes the first treatment cycle. The estimated DLT rates based on the Bayesian beta-binomial model will be provided for safety monitoring in the dose expansion cohort. If the DLT rate for the expanded dose level is equal or higher than 20% with a posterior probability of 80%, then the enrollment to the expansion cohort will be paused and the safety will be reassessed by the DEC. If the reassessment warrants, enrollment to the expansion cohort may be continued at the current dose level or 1 lower dose level. Safety evaluation will be conducted separately for induction, consolidation and maintenance phases.

With a non-informative prior, Beta(1,1) distribution, the numbers of DLTs for each cohort of 7 DLT-evaluable subjects, which trigger the enrollment pause for toxicities review, are listed in the following [table](#):

DLT-evaluable Subjects	Number of DLTs
7	3
14	4
21	6
28	8
35	9
42	11
49	12

DLT: dose-limiting toxicity

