1 INTRODUCTION

[figure not shown]
This Statistical Analysis Plan (SAP) contains a more technical and detailed elaboration of the principal features of the analysis described in the protocol, and includes detailed procedures for executing the statistical analysis of the primary, secondary and exploratory endpoints and other data.

The SAP is finalized and signed prior to any of the following: study unblinding, database hard lock, interim analysis, or accumulation of substantial amount of data in an open-label study to ensure lack of bias. For operational efficiency an earlier time is usually targeted. If needed, revisions to the approved SAP may be made prior to database hard lock. Revisions will be version controlled.

This statistical analysis is coordinated by the responsible biostatistician of GD-US. Any changes from the analyses planned in the SAP will be justified in the Clinical Study Report (CSR).

Prior to database hard lock, a final review of data and TLFs meeting will be held to allow a review of the clinical trial data and to verify the data that will be used for analysis set classification. If required, consequences for the statistical analysis will be discussed and documented. A meeting to determine analysis set classifications may also be held prior to database hard lock.

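### SAP 6.2.3 sets the phase 2 enrolment-pause threshold at a 25% DLT rate; the protocol's rule and trigger table use 20%, and with the protocol's prior and looks the two disagree at six of seven looks

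*SAP*

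**What the plan says.** The protocol gives the rule in the synopsis and again in section 7.1: "If the DLT rate for the expanded dose level is equal or higher than 20% with a posterior probability of 80" percent, enrolment to the expansion cohort is paused and the DEC reassesses safety. Section 7.1 also gives what is needed to apply the rule:

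- The prior and trigger counts: "With a non-informative prior, Beta(1,1) distribution, the numbers of DLTs for each cohort of 7 DLT-evaluable subjects" are tabulated as 3, 4, 6, 8, 9, 11 and 12 at 7, 14, 21, 28, 35, 42 and 49 subjects.
- The look schedule: "The DLT rate will be reviewed as the last subject of each cohort of 7 DLT-evaluable subjects completes the first treatment cycle".

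SAP 6.2.3 repeats the rule in nearly the same words but with a different number: "If the DLT rate for the expanded dose level is equal or higher than 25% with a posterior probability of 80" percent. It names the model ("The estimated DLT rates based on the Bayesian beta-binomial model will be provided for safety monitoring in the dose expansion cohort") but gives no prior, look schedule or trigger table. The SAP gives no reason for the change, and its revision history (section 8) does not mention it.

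**The concern.** Both texts are current and cannot both be applied. The SAP's version is the looser one, because it needs stronger evidence of toxicity before enrolment pauses. By its own introduction the SAP "contains a more technical and detailed elaboration of the principal features of the analysis described in the protocol", so it should not change a safety threshold without saying so.

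DLTs belong to a primary endpoint. Protocol 10.1 states that a data monitoring committee does not apply to this study, and this rule is the only numerical safety trigger given for phase 2. Someone who programs the model from SAP 6.2.3 would report that no pause is needed at counts where the protocol requires one. More patients could then be treated before the DEC looks at the data.

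**Working it through.** **Inputs.** Threshold t = 0.20 (protocol synopsis and 7.1) or 0.25 (SAP 6.2.3). Required posterior probability 0.80 (both documents). Prior Beta(1,1) and looks at every 7 DLT-evaluable subjects (Protocol 7.1 only). The SAP gives neither, so its threshold is evaluated here with the protocol's prior and looks.

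**Formula.** With x DLTs in n subjects the posterior is Beta(1+x, 1+n−x). The trigger is the smallest x with P(rate ≥ t) ≥ 0.80. For integer x, P(rate ≥ t) = P(Y ≤ x) with Y ~ Binomial(n+1, t).

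**Worked row, n = 14, x = 4.**
- t = 0.20: P(Y ≤ 4), Y ~ Bin(15, 0.20) = 0.0352 + 0.1319 + 0.2309 + 0.2501 + 0.1876 = 0.836. This is at least 0.80, so enrolment pauses.
- t = 0.25: P(Y ≤ 4), Y ~ Bin(15, 0.25) = 0.0134 + 0.0668 + 0.1559 + 0.2252 + 0.2252 = 0.686. This is below 0.80, so there is no pause.

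**All looks.**

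| n | Protocol trigger x | P(rate ≥ 20%) at x | P(rate ≥ 20%) at x−1 | P(rate ≥ 25%) at x | Trigger at 25% |
|---|---|---|---|---|---|
| 7 | 3 | 0.944 | 0.797 | 0.886 | 3 |
| 14 | 4 | 0.836 | 0.648 | 0.686 | 5 |
| 21 | 6 | 0.867 | 0.733 | 0.699 | 7 |
| 28 | 8 | 0.892 | 0.790 | 0.713 | 9 |
| 35 | 9 | 0.832 | 0.716 | 0.588 | 11 |
| 42 | 11 | 0.864 | 0.771 | 0.614 | 13 |
| 49 | 12 | 0.814 | 0.711 | 0.511 | 15 |

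At 20% the protocol's table reproduces in seven of seven rows: each listed count reaches 0.80 and one DLT fewer does not. At 25% the listed count reaches 0.80 only at n = 7. The SAP threshold needs 1 more DLT at n = 14, 21 and 28, 2 more at 35 and 42, and 3 more at 49.

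**Sensitivity to the prior.** With Beta(0.5, 0.5), Beta(0.2, 0.8) or Beta(0.25, 0.75) at the 25% threshold, the protocol's count still pauses only at n = 7.

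**Chance of ever pausing.** This is an exact binomial recursion in blocks of 7, using phase 2 data only. The true DLT rates are assumptions. Each cell gives the 20% rule, then the 25% rule.

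| True DLT rate | First three looks | First six looks | All seven looks |
|---|---|---|---|
| 20% | 0.37 vs 0.23 | 0.45 vs 0.26 | 0.48 vs 0.27 |
| 25% | 0.57 vs 0.40 | 0.70 vs 0.48 | 0.74 vs 0.50 |
| 30% | 0.74 vs 0.58 | 0.87 vs 0.71 | 0.91 vs 0.74 |

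The three-look column applies if the Simon design stops after stage 1 (22 subjects). That happens with probability P(X ≤ 11), X ~ Bin(22, p), which is 0.58 at a true CRc rate of 50% and 0.04 at 70%. The six-look column is the most relevant for a full trial: on a phase-2-only count, all 49 subjects are already enrolled at the seventh look.

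**Secondary check: who is counted.** Both documents put phase 1 subjects in the model; the protocol says "Subjects in phase 1 and phase 2 cohorts who complete the DLT observation period or experience DLTs will be included in the model-fitting process". The table ends at 49, the phase 2 maximum, and its column does not say whether the count is pooled. If pooled, the table is right as printed up to 49. If phase 1 subjects are added on top of the listed n, some listed counts no longer reach 0.80 at the 20% threshold:
- Assumed phase 1 result 0/3: the count falls short at n = 14, 21, 35 and 49 (0.716, 0.780, 0.759, 0.749).
- Assumed phase 1 result 1/6: it falls short at n = 14, 35 and 49 (0.769, 0.795, 0.783).

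**The case against.** The strongest reply is that the pause is a conduct rule. The protocol governs conduct and supplies a ready-made count table, so a committee using that table needs no posterior calculation and would never meet the SAP's figure. The result is also only a pause: after review, enrolment may continue at the same dose. In stage 1 the two rules agree at 7 subjects and differ by one DLT at 14 and at 21. The Simon test and the CRc estimate are untouched.

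Much of that is fair about consequences, but it does not remove the conflict. If the protocol governs, the SAP is the text to correct. The DEC Plan is not among the documents, so which threshold the committee would be shown is unknown.

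Three narrower objections stand:
- The SAP gives no prior or looks, so the six-of-seven count borrows the protocol's. It holds under the other priors tried.
- The look at 49 has no phase 2 enrolment left to pause on a phase-2-only count. Operationally the rules then differ at five of six looks, which narrows the gap only slightly.
- The dose rationale (Protocol 2.2.2) says no expansion dose level in an earlier gilteritinib monotherapy study "reached the threshold to stop enrollment (> 20% DLT with posterior probability of 80" percent). That concerns another study and is weak evidence of intent here. The reproduced table is sufficient without it.

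**Conclusion.** SAP 6.2.3 is wrong as written. Its 25% contradicts the 20% in the protocol synopsis and section 7.1, and the protocol's trigger table fits 20% in all seven rows, so 20% is not a slip in the protocol. With the protocol's prior and looks, the protocol's trigger count would not pause enrolment under the SAP threshold at six of seven looks. Over the six looks that can still affect phase 2 enrolment, the SAP threshold lowers the chance of ever pausing by 0.19, 0.22 and 0.16 at assumed true DLT rates of 20%, 25% and 30% (0.45 − 0.26, 0.70 − 0.48, 0.87 − 0.71). This must be corrected, because it is a decision threshold for patient safety. The question of whether the table counts pooled or phase 2 subjects is a clarification only, and the conclusion does not depend on it.

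**What to change.** Change 25% to 20% in SAP 6.2.3, and add there the Beta(1,1) prior, the review after every 7 DLT-evaluable subjects, and the protocol's trigger table. If the sponsor does intend 25%, amend the protocol synopsis and section 7.1 instead and replace the table with 3, 5, 7, 9, 11, 13 and 15. Check that the DEC Plan carries the same value.

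Also add one sentence saying whether phase 1 subjects at the recommended phase 2 dose count in the table's subject column. If they do, extend the table past 49. If they are added on top of it, recompute the triggers.

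The cost is one number, one copied table and one sentence in the SAP, with no patients and no new data. The threshold needs a protocol amendment only if 25% is the intended value.
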